#### 7.4.5 CONSERVATIVE FLUID MANAGEMENT PROTOCOL

Fluid management during shock or treatment for hypotension will be unrestricted. However, in patients not in shock, a conservative fluid approach will be recommended for all patients enrolled in the study (Table 4). This protocol is recommended for all enrolled patients, to be used until cessation of  $UF_{NET}$ .

**Table 4: Conservative fluid management protocol**

1.	Discontinue all maintenance intravenous fluids.
2.	Double concentrate or use lowest possible volume for all carrier fluids for medications, if possible.
3.	Continue enteral nutrition and free water flushes
4.	Manage electrolytes and blood products per usual practice.
5.	For shock, use any combination of fluid boluses and vasopressor(s) to achieve MAP $\geq 65$ mmHg as fast as possible.
6.	If the patient is on total parenteral nutrition (TPN), the TPN volume would be limited to provide the least volume required to administer the calories, protein, and lipids.

#### 7.4.6 RESCUE PROCEDURES

Our goal is to respect clinician autonomy and protect patient safety, while preserving separation of treatment between arms. Thus, we will encourage higher  $UF_{NET}$  rates beyond that which is specified by the protocol at the discretion of treating physician for emergent treatment of refractory hypoxia due to fluid overload or patient requiring massive volume infusion that requires control of fluid overload in the opinion of treating clinician (Table 5). However, following the resolution of emergency indication for fluid overload,  $UF_{NET}$  rate will be resumed as per protocol as determined by the attending nephrologist/intensivist. Being a feasibility randomized trial, the use of rescue rates of  $UF_{NET}$  will be collected as secondary outcomes and will not constitute a protocol violation.

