## 5.8 END POINTS

### 5.8.1 PRIMARY OUTCOME

The three primary feasibility outcomes are as follows:

1. *The between-group difference in mean delivered UFNET rate*: The primary objective is to measure a minimum of 0.53 mL/kg/h separation in the delivered patient mean UFNET rates between the restrictive and liberal UFNET rate groups. We chose between-group separation as a feasibility metric because it is a robust measure of adherence to complex protocols and has been used in ICU trials assessing the feasibility of frequently titrated interventions. Specifically, we reasoned that a larger study would not be feasible if the separation in the UFNET rates were less than 0.5 mL/kg/h. We chose 0.5 mL/kg/h as a clinically meaningful difference because our preliminary data indicated that a 0.50 mL/kg/h increase in UFNET rate is associated with increased mortality.
2. *Protocol adherence*: Adherence assessed by protocol deviation varies as the function of the definition of deviation and the frequency of measurements. Thus, in this trial, we will define protocol deviation *a priori* as delivered UFNET rate that lies >0.5 mL/kg/h outside of the target UFNET rate range in the assigned treatment group for greater than six consecutive hours during fluid removal *without* significant changes in MAP (*i.e.*, MAP <65 mmHg or  $\geq$ 90 mmHg). As such, out of range UFNET rates >0.5 mL/kg/h beyond the target UFNET rate range in the assigned treatment group will not constitute a protocol deviation when the bedside team titrated the UFNET rate as required to manage the patient hemodynamics (*i.e.*, when clinicians appropriately decreased rate or stopped fluid removal for hypotension; increased rate for hypertension or for treatment of respiratory distress due to fluid overload and pulmonary edema).

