**Table 5: Criteria for rapid rescue net ultrafiltration**

1.	Severe pulmonary edema with $\text{PaO}_2/\text{FiO}_2 < 150$ and $\text{PEEP} > 5 \text{ cm H}_2\text{O}$ due to fluid overload
2.	Respiratory distress due to fluid overload
3.	Ongoing hourly volume infusion at a rate higher than the assigned treatment group for more than 6 hours
4.	Inability to close surgical wounds due to tissue edema
5.	Failing spontaneous breathing trial due to fluid overload at the discretion of attending intensivist

$\text{PaO}_2$ , partial pressure of oxygen;  $\text{FiO}_2$ , the fraction of inspired oxygen;  $\text{PEEP}$ , positive end-expiratory pressure.

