## 10 DATA COLLECTION AND SITE MONITORING

### 10.1 DATA COLLECTION

At the UPMC and the Mayo Clinic, the research staff will collect data and record it either on paper data sheets and/or enter in a secure web database. Once daily, coordinators will enter data that can be analyzed for consistency.

In this trial, we will define protocol deviation as delivered  $UF_{NET}$  rate that lies  $>0.5$  mL/kg/h outside of the target  $UF_{NET}$  rate range in the assigned treatment group for greater than six consecutive hours during fluid removal *without* significant changes in MAP (*i.e.*, MAP  $<65$  mmHg or  $\geq 90$  mmHg). As such, out of range,  $UF_{NET}$  rates  $>0.5$  mL/kg/h beyond the target  $UF_{NET}$  rate range in the assigned treatment group will not constitute a protocol deviation when the bedside team titrated the  $UF_{NET}$  rate as required to manage the patient hemodynamics (*i.e.*, when clinicians appropriately decreased rate or stopped  $UF_{NET}$  for MAP  $<65$  mm Hg or increased rate for MAP  $\geq 90$  mm Hg).

We will also calculate “%on target” value for each center for each of the monitored variables (# of dates on-target for a specific variable/# of opportunities to be on-target for that specific variable). Principle Investigators at each site will receive monthly reports of (1) % on-target for each of the specific variables in the most recent month; (2) % on-target for each of the variables since the beginning of a trial; and (3) a list of dates/times from the past month, the specific data that were entered for those dates/times, and determinations of on- or off-target.

Investigators will use these reports to identify aspects of protocol management that can be improved at their sites. The on-target performances of all ICUs will also be included, allowing investigators at each center to know how their ICU is performing related to other ICUs. On-target performances will be discussed during regular meetings of the Steering Committee.

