### 4.2.2 PROTOCOL ADHERENCE

We have defined protocol deviation *a priori* as delivered UFNET rate that lies  $>0.5$  mL/kg/h outside of the target UFNET rate range in the assigned treatment group for greater than six consecutive hours during fluid removal *without* significant changes in MAP (*i.e.*, MAP  $< 65$  mmHg or  $\geq 90$  mmHg). As such, out of range UFNET rates  $>0.5$  mL/kg/h beyond the target UFNET rate range in the assigned treatment group will not constitute a protocol deviation when the bedside team titrated the UFNET rate as required to manage the patient hemodynamics (*i.e.*, when clinicians appropriately decreased rate or stopped fluid removal for hypotension; increased fluid removal rate for hypertension or for treatment of respiratory distress due to fluid overload and pulmonary edema).

We will report the following stratified by restrictive and liberal UFNET rate groups: i.) no. of occurrences of deviations for six consecutive hours divided by UFNET days (mean events per day); ii.) no. of days with UFNET out of range for at least six consecutive hours; iii.) no. of patients with at least one occurrence of UFNET rate out of range for six consecutive hours. The proportion of patients with protocol deviation will be compared using the Wald test for GLMM and adjusted for prespecified covariates.

As an exploratory analysis, we will also report the proportion of total hours of UFNET rate within, above, or below range for each patient weighted equally and proportionally to total hours of fluid removal.

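### The primary deviation rule (5.8.1, SAP 4.2.2) does not carry the rescue exemption of 7.4.6, so read literally it scores some permitted rescue as non-adherence, probably more often in the restrictive arm

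*Protocol*

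**What the plan says.** **Rescue policy.** Protocol 7.4.6 encourages rates above the assigned range, at the treating physician's discretion, for emergent fluid overload. It says that rescue use "will be collected as secondary outcomes and will not constitute a protocol violation". Table 5 lists five indications: (1) severe pulmonary edema with poor oxygenation, (2) respiratory distress, (3) "Ongoing hourly volume infusion at a rate higher than the assigned treatment group for more than 6 hours", (4) a surgical wound that edema keeps from being closed, and (5) a spontaneous breathing trial failed because of fluid overload.

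**Deviation definition.** Protocol 5.8.1 and SAP 4.2.2 define a deviation as a delivered rate more than 0.5 mL/kg/h outside the arm's range for more than six consecutive hours of fluid removal, without MAP below 65 or at or above 90 mmHg. On the upward side, 5.8.1 exempts "increased rate for hypertension or for treatment of respiratory distress due to fluid overload and pulmonary edema", and SAP 4.2.2 exempts "increased fluid removal rate for hypertension or for treatment of respiratory distress due to fluid overload and pulmonary edema". In both, the exemptions stand in a bracket opened by i.e., so the list reads as complete. Protocol 10.1 repeats the definition with a shorter bracket, whose upward part is "mm Hg or increased rate for MAP" at or above 90 mmHg.

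**Use in the analysis.** SAP 4.2.2 reports, by arm, the "no. of patients with at least one occurrence of" an out-of-range run. It then states: "The proportion of patients with protocol deviation will be compared using the Wald test for GLMM".

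**The concern.** The protocol gives one policy on rescue and two different exemption lists for one primary outcome, and neither list matches the policy. The analysis will follow SAP 4.2.2, which does not mention 7.4.6 or Table 5. A programmer working from the SAP would have no instruction to set aside a long rescue for, say, an abdomen that cannot be closed.

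One qualifying run is enough to classify a patient as a deviator. The trial exists to learn whether patients can be kept in their assigned range, above all in the restrictive arm. If a safety action that the protocol permits is scored as non-adherence, and the scoring threshold is much easier to reach in one arm, the between-arm comparison mixes adherence with the need for rescue.

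**Working it through.** **1. Coverage of the five indications, read literally**

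| Table 5 indication | 7.4.6 | 5.8.1 and SAP 4.2.2 | 10.1 |
|---|---|---|---|
| 1 Severe pulmonary edema | exempt | exempt | not named |
| 2 Respiratory distress | exempt | exempt | not named |
| 3 Ongoing infusion | exempt | not named | not named |
| 4 Wound closure | exempt | not named | not named |
| 5 Failed breathing trial | exempt | not named; arguably respiratory distress | not named |

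That is 5 of 5, then 2 of 5 (3 of 5 if a failed breathing trial is read as respiratory distress), then 0 of 5.

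**2. When indication 3 counts.** SAP 5.2.1.1 defines the delivered rate net of fluid infused in the current hour. In the example in 7.1 (PBW 70 kg, infusion 100 mL/h), a machine setting of 205 mL/h gives (205 - 100)/70 = 1.5 mL/kg/h, which is in range. The restrictive deviation line is passed only above 2.0 x 70 + 100 = 240 mL/h. Offsetting the infusion is therefore never a deviation; removal well beyond the offset can be.

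**3. Upper deviation lines** (top of range + 0.5)
- Restrictive: 1.5 + 0.5 = 2.0 mL/kg/h; at 70 kg, 140 mL/h.
- Liberal: 5.0 + 0.5 = 5.5 mL/kg/h; at 70 kg, 385 mL/h.

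**4. Where might rescue rates lie?** The documents do not say. As an assumption, take the maximum rates that U.S. practitioners report for stable patients in 5.2.6: 285 mL/h, IQR 200-341. The plan's own conversions reproduce: 285/80 = 3.56 and 341/80 = 4.26 mL/kg/h.
- At 80 kg the IQR is 200/80 = 2.50 to 4.26.
- At 70 kg it is 200/70 = 2.86 to 341/70 = 4.87, with median 285/70 = 4.07.

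All of these exceed 2.0 and lie inside the liberal range of 2.0-5.0. The exception is small patients: 341/5.5 = 62.0 kg, so below that PBW the upper quartile also passes the liberal line.

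**5. Weight of one patient.** With 56 per group (Protocol 4 and 9.1), one restrictive patient whose only qualifying run is a non-exempt rescue adds 1/56 = 1.8 percentage points. With the 72 per group still in SAP 3.6, it is 1/72 = 1.4.

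**6. Scale under assumed frequencies.** Suppose a share p of patients in both arms deviates for other reasons, and a share r of restrictive patients independently has a counted rescue, with none in the liberal arm. The extra restrictive deviators are 56 x (1 - p) x r.
- p = 0.30, r = 0.05: 56 x 0.70 x 0.05 = 2.0 patients (3.5 points).
- p = 0.10, r = 0.20: 56 x 0.90 x 0.20 = 10.1 patients (18 points).

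Both p and r are assumptions with no support in the documents. The range shows scale and is not a forecast.

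**The case against.** **7.4.6 already answers the question.** Its wording is general and makes no exception by indication, so it may well be meant to govern. A reader might infer that the plan definitely counts rescue under indications 3 to 5 as deviation. The documents do not settle that. They support only that SAP 4.2.2 as written would count it. The terms also differ: 7.4.6 speaks of a violation, while the outcome is a deviation. If the two mean the same, the SAP needs to say so; if they differ, 7.4.6 offers no protection.

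**The gap is narrower than three indications.** This largely stands. Indication 3 matters only beyond the offset, and indication 5 can be read as respiratory, so indication 4 is the one clear gap. Section 5.2.9 says the design already excludes patients with large infusions or wounds that cannot be closed. Exclusion applies at enrollment, however, and Table 5 and the safety outcomes both provide for an unclosable wound afterwards. The Trial Summary confines rescue to respiratory distress or severe hypoxia, which would nearly remove the mismatch, but Table 5 is the operative list and is wider.

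**Rescue is well recorded.** A reader who sees the YES/NO rescue item in 8.3.2 might infer that nothing else is collected. That is wrong: the same section records hourly rates, and its daily list records rescue rates beyond the assigned arm. Section 5.8.1 also records all reasons for non-adherence. What is not listed is the Table 5 indication with start and stop hours.

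**Little turns on it.** No document sets a success threshold for the deviation proportion, so no stated go/no-go decision changes. A rescue of more than six hours also meets the rescue outcome in SAP 5.2.2.4 (more than three hours), but reporting one event under safety and under adherence is not double counting in itself. Both points stand. The exploratory report of hours within, above and below range would show the excess, but not its cause.

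**Conclusion.** The mismatch is real and affects a primary outcome. As written, SAP 4.2.2 can score rescue that 7.4.6 permits as a deviation: clearly for wound closure, arguably for a failed breathing trial, and for infusion only when net removal exceeds the offset. In each case the run must exceed the range by more than 0.5 mL/kg/h for more than six consecutive hours at MAP 65-89 mmHg.

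The likely direction is to understate adherence in the restrictive arm, because its upper line is 2.0 mL/kg/h against 5.5. That is an inference from the two lines and from assumed rescue rates; the documents do not state it, and it weakens at low PBW. A reader might go further and infer a bias of known size. The documents do not support that, because they give no rescue frequency. What can be stated is 1.8 percentage points per affected patient at 56 per group. It should be fixed before analysis because the repair is small and the present text leaves a primary outcome open to two readings.

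**What to change.** Add one sentence to 5.8.1, 10.1 and SAP 4.2.2: *hours on documented Table 5 rescue, from its start until the indication resolves (7.4.6), are not counted as out of range.* State also whether such hours break a consecutive run.

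For each rescue, record the Table 5 indication (1-5) and the start and stop hour. These link to the hourly rates already collected.

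Report the deviation proportion by arm with rescue hours exempt (main analysis) and with rescue hours counted (sensitivity analysis). Leave the rescue outcome in SAP 5.2.2.4 as it is, and align the Trial Summary's rescue wording with Table 5.

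The cost is the added text, one short record per rescue and one extra analysis. The drawback is that the exemption depends on documentation, so hours could be over-labelled as rescue and hide poor adherence; the sensitivity analysis would show that. Access to rescue and the clinician's authority over the rate do not change.

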**Table 5: Criteria for rapid rescue net ultrafiltration**

1.	Severe pulmonary edema with $\text{PaO}_2/\text{FiO}_2 < 150$ and $\text{PEEP} > 5 \text{ cm H}_2\text{O}$ due to fluid overload
2.	Respiratory distress due to fluid overload
3.	Ongoing hourly volume infusion at a rate higher than the assigned treatment group for more than 6 hours
4.	Inability to close surgical wounds due to tissue edema
5.	Failing spontaneous breathing trial due to fluid overload at the discretion of attending intensivist

$\text{PaO}_2$ , partial pressure of oxygen;  $\text{FiO}_2$ , the fraction of inspired oxygen;  $\text{PEEP}$ , positive end-expiratory pressure.

#### 7.4.7 FACILITATING COMPLIANCE

We will use educational programs and academic detailing, automated reminders, selection of ICU staff that are local opinion leaders, and regular audit with feedback. Study coordinators will facilitate compliance in three key roles – background operational logistics, clinician in-servicing, and interventional logistics (e.g., ensuring CKRT machine is operational; suggested  $\text{UF}_{\text{NET}}$  rate is followed etc.). We will provide clear instruction guides to each coordinator and standardize work across ICUs.

### 8 DATA VARIABLES

#### 8.1 BACKGROUND ASSESSMENTS

1. Demographic and Admission Data (including age, sex, race and ethnicity, admission diagnosis including COVID status)
2. Pertinent Medical History and Physical Examination (including Elixhauser comorbidity index score)
3. Premorbid body weight and serum creatinine (if available)
4. Time on CKRT prior to enrollment
5. Type and location of ICU admission
6. Risk factors for AKI (sepsis, ischemia, nephrotoxin, other)
7. Risk factors for fluid overload (sepsis, heart failure, shock, trauma, massive transfusion)

#### 8.2 BASELINE ASSESSMENTS

The following information will be recorded during the 24-hour interval preceding study enrollment. If more than one value is available for this 24-hour period, the value closest to the time of study enrollment will be recorded. If no values are available from the 24 hours prior to enrollment, then values will be measured post enrollment but prior to initiation of study interventions. All values will be derived from clinically available data.

1. History and physical examination  
Vital signs: heart rate (beats/min), systemic systolic, diastolic, and mean arterial blood pressure (mmHg), body temperature (°C), central venous pressure (cm H2O), and other hemodynamic data (e.g., pulse pressure variation, stroke volume

variation, if available). Measured height and actual weight of the patient. Arterial blood gas values, if available.

2. CKRT mode, prescribed and actual blood flow rate, replacement fluid type and rate, dialysate type and rate, rate of ultrafiltration,  $UF_{NET}$  rate, effluent fluid rate, venous access and inflow pressures, transmembrane pressure, hemofilter type, time of last change of filter.
3. Administration of the following medications and fluids
  - a. Intravenous vasopressors and inotropes
  - b. Intravenous or enteral corticosteroids
  - c. Intravenous fluids and career fluids, enteral and parenteral nutrition
4. APACHE II score, including the acute physiology components and laboratory values
5. SOFA score: cardiovascular, kidney, respiratory, hepatic, and hematology organ function will be assessed using the SOFA methodology as described in [Appendix E](#).
6. Fluid intake and output before study enrollment and prior to ICU admission, if available.
7. If receiving positive pressure ventilation, ventilator settings including set tidal volume,  $FiO_2$ , and PEEP.

### 8.3 ASSESSMENTS DURING STUDY

#### 8.3.1 HEMODYNAMIC MONITORING DURING STUDY STARTUP

We will record the baseline hemodynamics before initiation of  $UF_{NET}$ , time at which  $UF_{NET}$  is initiated, time at which target  $UF_{NET}$  rate is reached. We will also record any episodes of hypotension, cardiac arrhythmias, administration of fluid bolus, vasopressor use, or increase in vasopressor dose.

#### 8.3.2 REFERENCE MEASUREMENTS

The following data will provide the basis for assessing protocol compliance and safety as well as between-group differences. Data for each of the variables will be recorded on the days shown in the Time-Events schedule ([Appendix F](#)) until death, discharge from the ICU, or day 28, whichever occurs first. Values will be derived from clinically available data.

1.  $UF_{NET}$  rate
  - a. Restrictive  $UF_{NET}$  rate group
    - i. Time and initial  $UF_{NET}$  rate
    - ii. Time and target  $UF_{NET}$  rate
    - iii. Time and hourly  $UF_{NET}$  rate

- iv. Reason and duration of UFNET hold (if any)
- v. Total volume of UFNET during the study
- vi. Rescue UFNET (YES/NO)
  
- b. Liberal UFNET rate group
  - i. Time and initial UFNET rate
  - ii. Time and target UFNET rate
  - iii. Time and hourly UFNET rate
  - iv. Reason and duration of UFNET hold (if any)
  - v. Total volume of UFNET during the study
  - vi. Rescue UFNET (YES/NO)

#### Reference measurements (Daily)

The following parameters will be measured and recorded between 4:00 A.M. and 10:00 A.M. using the values closest to 8:00 A.M. on the days specified in the Time-Events schedule. The following conditions will be ensured prior to measurements: no CKRT changes in the previous 30 minutes, no invasive procedures or ventilator changes for 30 minutes. All vascular pressures will be zero-referenced to the mid-axillary line.

1. If receiving CKRT: CKRT mode, blood flow rate, actual rate, replacement and dialysate flow rate, ultrafiltration rate, UFNET rate, effluent flow rate.
2. If receiving positive pressure ventilation set tidal volume, FiO2, PEEP, and plateau pressures.
3. PaO2, PaCO2, pH, and SpO2
4. Rescue procedures used
  - a. Rescue UFNET rates used beyond the assigned treatment arm
  - b. Vasopressors used for hypotension including dose
  - c. Fluid bolus used for hypotension including volume
5. Serum electrolytes
6. Administration of the following fluids and medication
  - a. Enteral or intravenous corticosteroids
  - b. Intravenous vasopressors
7. Was CKRT interrupted? (YES/NO)
8. Cardiovascular SOFA score
9. Fluid intake and output

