## F. TIME-EVENTS SCHEDULE

### F1. GENERAL DATA COLLECTION

Measurement/Event	Screening	Baseline/ Day 0@	1	2	3	4	5	6	7	8- 14	15- 21	22- 28
Serum Creatinine	X	X	X	X	X	X	X	X	X	X	X	X
Demographics, History and Physical		X										
AKI Cerner alerts	X	X										
Etiology of AKI		X										
APACHE II		X										
Weight*		X	X	X	X	X	X	X	X	X	X	X
Daily FB*		X	X	X	X	X	X	X	X	X	X	X
Restrictive UF NET		X	X	X	X	X	X	X	X	X	X	X
Liberal UF NET		X	X	X	X	X	X	X	X	X	X	X
Ventilator parameters ΦΨ*		X	X	X	X	X	X	X	X	X	X	X
CKRT parameters ΦΨ\$		X	X	X	X	X	X	X	X	X	X	X
ABG*		A	A	A	A	A	A	A	A	A	A	A
Fluids (intake/output)*		X	X	X	X	X	X	X	X	X	X	X
MAP*		X	X	X	X	X	X	X	X	X	X	X
CVP, CI, PPV, SVV, and other hemodynamic data*		A	A	A	A	A	A	A	A	A	A	A
Hypotensive & Hypertensive episodes \$%		X	X	X	X	X	X	X	X	X	X	X
Cardiac arrhythmias \$%		X	X	X	X	X	X	X	X	X	X	X
Use of rescue UF NET rates \$		X	X	X	X	X	X	X	X	X	X	X
Severe hypophosphatemia\$		X	X	X	X	X	X	X	X	X	X	X
Severe hypokalemia\$		X	X	X	X	X	X	X	X	X	X	X
Severe hypocalcemia		X	X	X	X	X	X	X	X	X	X	X
All lab data*		X	X	X	X	X	X	X	X	X	X	X
Vital signs and medications*		X	X	X	X	X	X	X	X	X	X	X
Inability to close surgical wounds		X	X	X	X	X	X	X	X	X	X	X
New organ dysfunction*		X	X	X	X	X	X	X	X	X	X	X
Secondary infections		X	X	X	X	X	X	X	X	X	X	X
SOFA score β*	X	X	X	X	X	X	X	X	X	X	X	X
Vital status		X	X	X	X	X	X	X	X	X	X	X

Measurement/Event	Screening	Baseline/ Day 0@	1	2	3	4	5	6	7	8- 14	15- 21	22- 28
KRT Status		X	X	X	X	X	X	X	X	X	X	X
IHD use			X	X	X	X	X	X	X	X	X	X

X= Required

A=When available

Ψ=Data gathered at times indicated or until 72 hours, whichever occurs first

β=Records clinically available creatinine, platelets, bilirubin, MAP, SBP, FiO2, fluid bolus and vasopressor use

ϕ=Measure during reference period (0600 -1000); other values may be obtained closest to 0800 on the specified calendar date

\* = collected only if the patient is still in the ICU before day 28 and if available in the electronic health records

\$\_= collected only if the patient is on CKRT upto 24 hours following discontinuation of CKRT

%=collected only if the patient is on IHD

@ =Data collected before initiation of study intervention

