#### 5.2.1.4 *Organ failure free days to day 28*

Organ failure is defined as present on any date when the most abnormal vital signs or clinically available lab value meets the definition of clinically significant organ failure according to SOFA scores. Patients will be followed for development of organ failures to death, hospital discharge or study day 28, whichever comes first. Each day a patient is alive and free of a given organ failure will be scored as a failure-free day. Any day that a patient is alive and free of all organ failures will represent days alive and free of all organ failure.

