##### 5.2.1.4.1 E. SOFA scoring system

Variables	Sequential Organ Failure Assessment Score				
	0	1	2	3	4
Respiratory					
PaO 2 /FiO 2 (mmHg)	>400	≤400	≤300	≤200 a	≤100 a
Coagulation					
Platelets (x 10  /µL)	>150	≤150	≤100	≤50	≤20
Liver					
Bilirubin	<1.2	1.2 – 1.9	2.0 – 5.9	6.0 – 11.9	>12.0

Cardiovascular					
MAP (mmHg)	$\geq 70$	$<70$			
Vasopressor b (doses in mcg/kg/min)			Dopamine $\leq 5$ OR Dobutamine (any dose)	Dopamine $>5$ OR Epinephrine $\leq 0.1$ OR Norepinephrine $\leq 0.1$	Dopamine $>15$ OR Epinephrine $>0.1$ OR Norepinephrine $>0.1$
None	None				
Central Nervous System					
Glasgow Coma Scale	15	13 – 14	10 – 12	6 – 9	$<6$
Kidney					
Creatinine (mg/dL)	$<1.2$	1.2 – 1.9	2.0 – 3.4	3.5 – 4.9 OR $<500$	$\geq 5$ OR $<200$
Urine output (mL/day)					

a Values are with ventilatory support; the maximum score in patients not receiving ventilatory support is 2

b Pressor agents administered for at least 1 hour

We define a clinically significant organ failure as a new SOFA score of  $\geq 2$

We treat post-ICU SOFA as normal; post-ICU means getting out and staying out of ICU

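### The protocol takes daily SOFA inputs nearest 8 A.M., the SAP scores organ failure on the worst value of the date, and nothing reconciles the two

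*Protocol*

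**What the plan says.** Protocol 8.3.2, under Reference measurements (Daily), sets the timing rule: "The following parameters will be measured and recorded between 4:00 A.M. and 10:00 A.M. using the values closest to 8:00 A.M". It adds conditions to be met before the reading: "no CKRT changes in the previous 30 minutes, no invasive procedures or ventilator changes for 30 minutes". The items under this rule include:

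- "Cardiovascular SOFA score";
- PaO2, and FiO2 for patients on positive pressure ventilation;
- "Vasopressors used for hypotension including dose";
- "Fluid bolus used for hypotension including volume".

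SAP 5.2.1.4 (organ failure free days) uses a different daily value: "Organ failure is defined as present on any date when the most abnormal vital signs or clinically available lab value meets the definition". The threshold is in the notes to the SAP SOFA table: "We define a clinically significant organ failure as a new SOFA score of" 2 or more. SAP 5.2.2.7 bases new organ dysfunction on change in SOFA, with a cardiovascular score going from 3 to 4 as its example.

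Protocol Appendix F1 has a SOFA row. Its footnote lists clinically available components, with neither a clock time nor a worst-value rule. A separate footnote reads: "Measure during reference period (0600 -1000); other values may be obtained closest to 0800 on the specified calendar date".

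**The concern.** A value near 8 A.M. is not a worst-of-day value. A coordinator who follows 8.3.2 as written enters the wrong input for the SAP variable, and no passage of the protocol asks for the worst value.

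The 30-minute conditions suit machine and ventilator settings but not organ-failure scoring. The first step in protocol Table 3 for hemodynamic instability is to stop fluid removal. If that counts as a CKRT change, which the documents do not say, a reading in the next 30 minutes is ruled out.

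At stake are organ failure free days and new organ dysfunction. Both could be under-counted for short episodes, and both could be abstracted differently from one ICU to another.

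**Working it through.** The plan states no figure on this point, so there is none to reproduce. The check compares the rules, then gives an illustration of size.

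**Which value feeds SOFA**

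| Source | Items | Daily value |
|---|---|---|
| Protocol 8.3.2, daily list | Cardiovascular SOFA, PaO2, FiO2, vasopressors with dose, boluses | Closest to 08:00, within 04:00-10:00, after 30 minutes without the listed changes |
| Protocol Appendix F1, SOFA row | Clinically available components, including MAP, FiO2, bolus and vasopressor use | Not stated |
| Protocol Appendix F1, reference-period footnote | Marked on ventilator and CKRT rows; other values may also be taken near 0800 | 0600-1000 |
| SAP 5.2.1.4 | All SOFA organ failures | Most abnormal on the date |

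The first and last rows conflict, and the middle rows do not settle the matter. The two reference windows also differ: 04:00-10:00 in 8.3.2 and 0600-1000 in F1.

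**Which SOFA components are exposed**

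- Cardiovascular: in both SOFA tables, MAP below 70 mmHg alone scores 1, which is under the threshold of 2. Failure therefore turns on vasopressor or inotrope agent and dose, given for at least 1 hour. The step from 3 to 4 can depend on norepinephrine or epinephrine crossing 0.1 mcg/kg/min. The F1 SOFA footnote names vasopressor use but not dose, and SAP 5.2.1.4 speaks of vital signs and laboratory values without naming vasopressors.
- Respiratory: PaO2 and FiO2 are both in the 8 A.M. list.
- Platelets, bilirubin, creatinine and Glasgow Coma Scale are not in that list, so 8.3.2 creates no conflict for them.

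**Illustration of size**

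Assume one qualifying episode of h hours at a uniformly random clock time, with 8.3.2 as the sole source. The documents give no episode durations, so a range is shown.

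- One reading at 08:00: P(caught) = h/24.
- Any value in 04:00-10:00 counted: P = min(1, (6 + h)/24).
- Any value in 06:00-10:00 counted: P = min(1, (4 + h)/24).

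| h (hours) | Single reading | Any in 04:00-10:00 | Any in 06:00-10:00 |
|---|---|---|---|
| 1 | 1/24 = 4% | 7/24 = 29% | 5/24 = 21% |
| 2 | 2/24 = 8% | 8/24 = 33% | 6/24 = 25% |
| 4 | 4/24 = 17% | 10/24 = 42% | 8/24 = 33% |
| 8 | 8/24 = 33% | 14/24 = 58% | 12/24 = 50% |
| 12 | 12/24 = 50% | 18/24 = 75% | 16/24 = 67% |
| 24 | 100% | 100% | 100% |

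The loss is large for short episodes and nil for continuous support. The effect of the 30-minute conditions cannot be quantified from the documents.

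**The case against.** The strongest reply is that 8.3.2 is not the only source. In Appendix F1 the reference-period mark sits on the ventilator and CKRT rows alone. SOFA, MAP, blood gases, all laboratory data, vital signs and medications, and new organ dysfunction have rows without it. The 8.3.2 list also contains fluid intake and output and whether CKRT was interrupted, which make sense only as daily records. It may be a loosely worded daily form, not a rule to ignore the rest of the day.

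Much of this stands, and it rules out three stronger readings that a reader might infer:

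- That daytime organ failures are missed. The unmarked F1 rows could supply them, so the documents support only that they may be under-counted.
- That rescue UFNET and hypotension are lost. Section 8.3.2 itself also records hourly UFNET and a yes/no rescue item. F1 has a rescue row, and protocol 13.1 puts rescue on the case report form. The SAP 5.2.2.4 rule of more than 3 consecutive hours can be derived from hourly rates. Hypotensive episodes have their own F1 row, and SAP 5.2.2.1 counts new or increased vasopressors and boluses.
- That the difference between strategies is biased toward nil. That is plausible if under-capture is similar in both groups, but the documents do not show it.

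These routes still do not close the SOFA gap. F1 gives no worst-value rule, and its footnote lets other values be taken near 0800. Its hypotension row is tied to CKRT (up to 24 hours after stopping) or IHD, whereas organ failure free days run to death, hospital discharge or day 28. The protocol 13.1 entry for hypotension is limited to episodes judged related to the rate of fluid removal or of uncertain relationship. Nor does an episode record necessarily hold the maximum vasopressor dose that cardiovascular SOFA needs.

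**Conclusion.** The protocol and SAP conflict on which daily value feeds the cardiovascular and respiratory SOFA components, and Appendix F1 does not resolve it. Organ failure free days and new organ dysfunction may be under-counted for short vasopressor-dependent or hypoxemic episodes. The capture percentages are not estimates of actual loss, because they rest on random timing and on 8.3.2 as the sole source.

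The consequence is limited. No primary outcome is affected. SAP 4.3 treats secondary outcomes other than mortality and KRT dependence as exploratory, and protocol 11.3 says the trial is not powered for adverse-event differences. The point still deserves correction, because protocol 11.7 names the effects on secondary and safety outcomes among the things to be learned, and the change is cheap.

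**What to change.** In protocol 8.3.2 and Appendix F1:

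- Limit the 8 A.M. reading and its 30-minute conditions to CKRT and ventilator settings.
- Collect SOFA inputs as the most abnormal value per calendar day, including PaO2/FiO2 and the highest vasopressor dose given for at least 1 hour.
- Record vasopressors and boluses over 24 hours, as any use or as totals.
- State one reference window in place of 04:00-10:00 and 0600-1000.

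In SAP 5.2.1.4, name vasopressor dose alongside vital signs and laboratory values, so that the cardiovascular component is covered.

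The cost is wording in the protocol, SAP and case report form, and slightly more abstraction per ICU day. Protocol 8.3.2 already takes its values from clinically available data, so no new measurement is needed.
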